7.0 Privacy and Confidentiality

- This study will obtain and keep confidential subjects' Protected Health Information (PHI).
- All study personnel with access to PHI will be required to maintain current required trainings and follow protocol for maintaining records according to best practices (i.e. locked file cabinet, locked safe when not on VA premises and Authorization to Transport on file, only study personnel access to drives or other e-locations of data)

8.0 Communication Plan

- The Coordinating site will be in charge of all CIRB communications and will assure submission of required documents. The Project manager will meet regularly with all sites to ensure local notification and R&D approvals are obtained and remain current.

- Any changes to the protocol or HIPAA documentation will be discussed with participating sites and submissions/approvals will be communicated to each site as they are completed and obtained.
- Any SAE or AE will be communicated from the Local Site and reported to the CIRB as outlined based on specifics of the events. Interim results and reports, such as DSMB will be forwarded to each of the participating sites in a timely manner.
- Each participating site will be provided with a copy of the approved protocol; and will receive updates as they occur.
- Bedford PI will communicate with the LSI's regarding timing of site closures.

HSR&D Data and Safety Monitoring Board
Data Analysis Plan (DAP) v1

PI: [name]

Title: Continuing the Conversation: A Multi-Site RCT Using Narrative Communication to Support Hypertension Self-Management for African American Veterans – (IIR 17-185)

Table of Contents

Background	2
Rationale for Study Sample Size	2
Data Collection	2
Randomization	4
Interim Data Analysis	4
Missing Data/Subject Dropouts	4
Covariates for Adjustment Models	4
Data Transformations	4
Analytical Sets	4
Monitoring Adverse and Serious Events	4
Analysis Plan	5
Power Calculations	6
Cost Analysis	7

Background

This is a randomized controlled trial aimed at improving hypertension self-management and lowering blood pressure (BP) in African-American Veterans. In previous HSR&D-funded work, we created video-recorded stories told by African-American Veterans with hypertension, in which Veterans shared strategies for effective self-management. In this study, we 'begin the conversation' by showing these videos to Veteran participants, inviting them to select the peer narrative that is most compelling. We then 'continue the conversation', offering longitudinal support via 6 months of narrative-aligned text messages. Texts will cover key subject areas, providing education, reminders and periodic assessments, and include quotations derived from and aligned with transcripts from the chosen narrative. We will measure the intervention's impact on BP, self-efficacy and self-management behaviors, and conduct a cost analysis.

Rationale for Study Sample Size

We will pilot the process of providing in-person guidance to 20 Veterans as they (a) View the Veteran videos; (b) Select a preferred video narrative; and (c) Sign up to Get texts through the HealtheDialog Texting system. The pilot will contain usability testing and a formative evaluation of the Veterans' experiences. We will purposefully sample 10 Veterans from each site (total of 20) and will aim to include 4 women Veterans (2 per site). We will pilot the process of (1) guiding the Veteran in selection of a preferred veteran storyteller after viewing all stories; (2) using this choice to inform selection of a texting protocol; (3) Receipt of 1 month of texts; and 4) follow-up assessment at the end of 1 month. We will assess feasibility of two options for Veterans to access texts: (a) via regular texting, available on all text-enabled phones; (b) via HealtheDialog 'App' which allows study team tracking of text opening (but is available only on Smart phones). We will assess completion rates (how many Veterans have difficulty or discontinue texts early) and perceptions (e.g. "I felt connected to the storyteller while receiving texts", "the number of texts was: too few, just right, too many"). The formative evaluation will include a qualitative interview with all Veteran participants to understand their experiences with the CTC protocol. Our semi-structured interviews will cover their overall experiences, as well as specific questions about the enrollment process, frequency and content of messages. Interviews will be audio-recorded with brief, descriptive field notes. We will then Test CTC by conducting a randomized controlled trial with the following setting and sample: 600 African-American Veterans with poorly controlled hypertension. Veterans will be recruited from two VA healthcare sites with known disparities in hypertension control.

Data Collection

We will seek a HIPAA waiver from the IRB for data access in order to identify potential participants. • We will include Veterans who have been receiving care at the recruiting VA site for ≥ 1 year prior to recruitment, with 2 or more visits documented over the past year. We will include Veterans who have documented HTN (ICD10 diagnosis codes: I10-essential HTN) during this 1-year period. We will include only patients who self-identify as African American or Black. In addition, participants must be on at least one medication for BP. Eligible participants will need to have access to their own or a family member's cell phone or smart phone for participation and they must be willing to use this phone for receipt of text messages over a 6-month period. We will exclude Veterans who participated in our previous VA Stories study.

We will exclude patients based on responses from the screening questionnaire conducted during the initial phone call, which screens for cognitive disabilities that might prevent them from

actively or reliably participating in the interviews. We will include both women and men in the study; given that 5% of the VA patient population is women, we plan to oversample for women in order to expect a similar proportion of women to participate in the study. Based on our response rate in previous studies we are confident that approximately 70% of patients will agree to participate. We will track demographics and co-morbidities and BP level, as well as reasons for refusal for those who decline participation. We will delete PHI on potential participants who decline or who do not respond from our analytic database.

For each potentially eligible patient, the RA will contact the patient by telephone, explain the study and ask several eligibility screening questions including the patient's race/ethnicity. We will include only patients who self-identify as African-American or Black. Then the RA will ask if the patient wishes to participate and will schedule a time for the patient to come to the clinic. We have had success in multiple prior studies using this procedure.

As listed in the table below, we will collect 7 data elements: (1) Veteran characteristics; (2) Intervention dose/exposure; (3) Narrative Communication measures; (4) Social Cognitive-Theory-based measures; (5) Hypertension management behaviors; (6) Blood Pressure (BP) (blood pressure will be checked by RA at in-person visits at baseline and at 6 month follow up); and (7) Implementation Data including Process Measures and measures of Fidelity. We will gather these elements through initial data collection (CDW), over-the-phone screening survey, baseline visit and follow-up visit observations and surveys, texting system and phone calls to participant.

• Table 8. Seven Key Data Elements		Timing	Source
1. Veteran Characteristics			
Participant Demographics		1	S,C
Comorbidities, VA Utilization		1	C
2. Intervention Dose/Exposure			
Number of videos watched and time spent viewing		2	S
Which was selected video?		2	S
3. Narrative Communication			
Video Transportation Scale		2	S
Homophily (personal relevance)		2	S
4. Social Cognitive Theory			
Beliefs About Medications (BMQ)		1,4	S
Self-efficacy for hypertension (e.g.: MASES-R, PEPP)		1,4	S
5. HTN management behaviors			
Avoid Salt, Be Physically Active, Monitor your BP(H-SCALE, PEMH)		1,4	S
Talk with your doctor (H-SCALE)		1,4	S
Take Your Medicines: Morisky ; and administrative data adherence (MPR)		1,3,4	S, C
6. Primary Outcome (H1)			
Measured BP (systolic/diastolic)		1,4	BP, C
7. [Implementation Data/ Process Measures/Fidelity]		3,4	RA, S, T
Text message opening (subgroup)		3	T
Responses to text assessment		3	T
Confirmation of text receipt		4	S
Phone calls for texting assistance		3	RA
Staff time spent for implementation		3	RA
Persistence/Early Discontinuation of Texting Protocol		3	T
Reasons for discontinuation		5	P

1=Baseline, 2=Immediately post-Video Viewing; P, 3=Repeated throughout 6-month study period, 4 = six-month follow-up; 5= phone call to drop-out.

Source: S = Survey; C = CDW data; RA=Research assistant; T=Texting System; P=phone call to participant; BP = Blood pressure cuff, standard protocol

Randomization

Random allocation to CTC or control will be stratified by site, and within each site, we will stratify by sex (women/men). Our statistician will create a randomization table with randomization blocks varying between 5 and 10 subjects.

Interim Data Analysis

We do not plan to conduct interim data analysis

Missing Data/Subject Dropouts

Missingness not at random may introduce bias. Advance planning through sound data collection and quality control will be used to minimize this bias. We will use all available data regardless of whether a patient has a complete record. Group means will be reported as least-squares means, the predicted marginal mean values, or those that would be expected with a balanced design. Participants with missing data will be compared to those without. Inverse probability weight in and pattern-mixture modeling using the longitudinal data structure, for non-ignorable missing data, will be considered.

Covariates for Adjustment Models

We will look at the balance of randomization and adjust for demographics and behavioral variables if imbalanced.

Data Transformations

N/A

Analytical Sets

We intend to include all patients in intent to treat analysis.

Monitoring Adverse and Serious Events

Because this is a low-risk trial of an educational DVD, we do not expect SAE's or AE's. We will plan to report any SAE's defined as death of participant or hospitalizations reported at 6-month follow-up.

At the time of recruitment, patients experiencing hypertensive urgency, as defined by JNC as Blood Pressure Systolic \geq 180 OR Diastolic \geq 120, regardless of symptoms, will be referred to urgent care and a notification letter will be sent to their primary care physician. If a patient reports symptoms related to the hypertensive urgency, even if before viewing the intervention DVDs, this will also be reported as an AE. AE's also include stress related to watching the DVD. All AE's reported at baseline and 6-month follow-up will be recorded and submitted at Continuing Review.

Analysis Plan

We will first identify key distributional features for all variables of interest (non-normality, skewness, ceiling or floor effects, presence of implausible values, outliers, etc.) and calculate descriptive statistics. We will document recruitment and retention with a CONSORT diagram. Following best practice, baseline differences between intervention and comparison groups will be based on standardized differences, not simply tests of statistical significance. All primary hypotheses will be tested by intent-to-treat; secondary analyses will account for important covariate imbalances between groups, levels of adherence to the intervention protocol, and missing data. All analyses will be two-sided, with alpha error = 0.05.

Hypothesis 1: (Primary Hypothesis) The difference in blood pressure from baseline to 6 months will favor CTC intervention group by 5mm Hg, compared with the change in control.

H1 postulates a difference-in-differences between study groups. We will use study group, assessment time, and group-time interactions as predictors in regression models. With this parameterization, the coefficient for the group-time interaction represents differential change for intervention vs. comparison. Multilevel mixed-effects generalized linear models will: (1) model the outcome distribution with an appropriate link function; (2) account for clustering of repeated measures within individual; (3) adjust for observed group imbalances as secondary analyses; and (4) support secondary mediation analyses as described below. The most general structure of the mixed model is $y = X\beta + Z\gamma + \epsilon$, where the y matrix is the observed outcomes, β is a vector of fixed-effect parameters with design matrix X , γ is a vector of random-effect parameters with design matrix Z , and ϵ is a random-error vector. We will assume that γ is independent of ϵ and has a multivariable normal distribution with mean $\mathbf{0}$. We will examine residuals to seek gross violations of underlying assumptions, and explore approaches to address violations such as variable transformation, outlier trimming, or placing bounds on the extent that extreme observations can affect conclusions.

Hypothesis 2: Self-efficacy and hypertension management behaviors during 6-month follow-up will be greater for those in the CTC intervention group than comparison.

As Self-efficacy and HTN management behaviors (salt intake, physical activity, doctor-patient interaction, monitor BP) will be measured as self-report at baseline and follow-up, we can measure these as differences in change ("difference-in difference") between study groups, and mirror the analysis plan for H1.

In addition to self-report, for "Take your medicines" (medication adherence) we will use administrative data to calculate refill-based measures (ie: MPR) for each HTN medication and average these over six-month periods (before and during intervention). We will again use a repeated measures analysis (like H1).

Secondary Analyses: Covariates to account for substantial imbalances in group characteristics will be added to our main regression models. Secondary analysis will occur for the separate measures of HTN management behaviors and BP change. As in our prior trials, we will also conduct secondary stratified analyses above and below the median mean arterial pressure at baseline (in our prior VA stories, we found the effect greater in those below the median baseline BP (see Section B5.b)). We will also analyze effect by site, by chosen storyteller and by age group. Further, using the administrative data for MPR, we have a pragmatic opportunity to study sustainment of effect after the six-month CTC is completed. For the subset of patients with six-months completed before Year 4, we will also calculate MPR six months after the end of CTC. In a secondary model, three time periods (before, during, after CTC) will be jointly tested using "segmented regression" to account for the three time periods.

Hypothesis 3: The effect of CTC on BP will be mediated by the more proximal measures of (H3a) cognitive and emotional processes (i.e.: emotional engagement with stories, self-efficacy), and (H3b) HTN management behaviors.

For this hypothesis, we will conduct a formal mediation analysis. Initial methods will follow Barron and Kenny's

protocols, with more recent advances developed by MacKinnon. Mediation occurs when an intervention changes the rate of uptake of an intermediate process that directly influences outcome. Mediation analysis can help to disentangle the mechanisms which may contribute to intervention effectiveness. We will estimate the proportion of the intervention effect that is transmitted through each of these mediators and quantify the precision of these estimates with 95% bias-corrected and accelerated bootstrap confidence intervals. Thus, we will be able to quantify the relative proportional mediation for each of the measures listed in Hypothesis 2.

Power Calculations

Power is driven by our most distal outcome, Blood Pressure (H1). Our sample size calculations are performed to detect a difference in the change in BP, comparing intervention and control. We carry out the calculations to determine sample sizes that would detect significant effects at the 2-sided 0.05 level, at 80% power. Difference in BP for our video stories alone ranged up to 6mm Hg, and as low as 2.7mm Hg (adjusted difference in systolic BP in VA stories). We have designed CTC to result in a stronger effect, compared with our prior VA Stories. With this rationale in mind, we calculated power to achieve a conservative and meaningful difference of difference in BPs of 5mm Hg. We used a repeated measure power calculation to estimate the group-time interaction for the difference of differences statistical analysis. Derived from our prior work, follow-up rates, within-person correlation of repeated measures of BP and standard deviation of a single BP measurement were used for the estimates. With our recruited sample of 600 (and assuming follow-up rates, over-time within-person correlation, and BP standard deviations from our prior work (85% follow-up, correlation = 0.5, SD = 18 (equivalent to variance of 324)), we have over 80% power (alpha 0.05) to detect a difference of 5mm Hg. In fact, we calculated power for a range of scenarios, and are able to maintain the 5mm Hg detection with a lower follow-up rate of 82%.

Power for H2 & H3: Conceptually, the CTC intervention impact on blood pressure is possible because the intervention will have an effect on more proximal cognitive and behavioral outcomes (H2) that then mediate the main effect (H3). Thus, theoretically, power for group-by-time differences in the scales for H2 will be greater than H1, and thus we should be over-powered for these measures. We calculated H2 power for difference-in-differences analyses. As each of the scales were different, we report minimum detectable differences as effect sizes. For example, Morisky Medication Adherence Scale (MMAS) response categories are yes/no for each item with a dichotomous response and a 5-point Likert response for the last item. The MMAS categorizes low adherence as a score of <6, medium adherence as a score of 6 to <8, and high adherence as a score of 8. In a 2008 publication validating MMAS in a complex patient population (with 75% African American and 54% with an income < \$5,000), mean score was 6 (SD 1.6). We found similar mean (SD) in our prior storytelling interventions. A one-point MMAS shift has been reported as clinically important (which translates to an effect size (r) = 0.29 assuming the mean and SD above). Repeating our repeated measures power calculations formulas from Aim 1, with a follow-up of 80%, we have 80% power (alpha 0.05) to detect an effect size of 0.29 with an over-time correlation coefficient as low as 0.3, and each MMAS administration SD as high as 3.0. This estimate is conservative as the SD is over-estimated, and the correlation over time will likely be higher. Thus, we are more than powered to detect an effect size of 0.29 for MMAS, and by extension our other H2 scales.

Further, for H3, our simulation studies (Fritz and MacKinnon) show that a total sample as small as 200 is adequate for 80% power with standardized effect sizes for the mediation paths of 0.29 or larger. Thus, we have considerable power to detect small effects in the mediation analyses.

Cost Analysis

We will conduct a cost-identification analysis (CIA) to assess the cost of providing the CTC, and a budget impact analysis (BIA) to assess impact on costs to a VA medical center of implementing the intervention. To estimate costs and the potential budget impact for a facility implementing CTC, we will obtain cost data from VA Managerial Cost Accounting (MCA) datasets (formerly known as Decision Support System (DSS) National Data Extracts), consultation with the Health Economics Resource Center, and consultation with the study sites. Costs will be tracked for each intervention component: viewing stories, selecting preferred narrative, and delivering text messages. We anticipate that the majority of costs will be related to staff time. In addition, we will also estimate the staff time associated with the control group. To obtain staff time estimates, we will have RAs track the time needed for each intervention component, and also for the control group. RAs will in addition track time spent handling phone calls for assistance with the texting system for both intervention and control (we will maintain a phone line during recruitment and follow-up). Additionally, we will describe the number and types of staff positions required for the intervention and control. We will then estimate wages based on staff positions using data obtained from the facility. We will use a similar process to estimate the training costs related to staff time. In addition to staff time, we will estimate the costs of supplies for showing the videos, training staff, and the toolkit (training guides and Veteran handouts). The Aim 3 economic analyses will be primarily descriptive statistics. Using the cost estimates of supplies, staff time, and the potential savings to the healthcare system that result from the intervention (e.g., decreases in missed appointments, ED visits, or HTN-related hospitalizations), we will calculate the budget impact of implementing the intervention from the perspective of the facility. We will follow the guidelines outlined for best practices in BIA. We will create tables to describe the assumptions of our inputs and outputs, and perform sensitivity analyses to examine how changing the model assumptions impacts the potential costs for the facility.

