SELECT a Preferred Veteran Storyteller: After the Veteran has viewed the videos, the Veteran will complete the final brief section of the survey. If necessary the RA will re-contact via phone or by text at that time to ask survey questions. The RA will remind participant of the five storytellers they just watched. If at that time the Veterans wish to pause and go back to see any videos they missed or re-view any videos, they may. The RA will explain that this selection will inform the content of the text messages sent to the Veteran over the upcoming 6 months, with the goal of providing text messages that work well for the Veteran. The RA will explain that some messages will include either (a) direct quotes from this storyteller, referencing back to or building further upon the video-recorded story; or (b) references to topics related to those which the Veteran talked about. **If participant is not reached following watching the storyteller videos, the site coordinators will initiate a text requesting that they select a storyteller. If they do not reply to the text request and are still unreachable 2-weeks after the baseline visit occurs, we will select a storyteller for them by selecting, in order, from a list of the 5 storytellers; when all 5 have been assigned in this way, we will start back at the top of the list. Lists will be maintained separately at the two sites. Participants will be told during the baseline visit, once assigned to intervention, after watching the videos that if they do not select a storyteller for some reason, they will be assigned one by the research team.**

GET preference-based, narrative-aligned CTC texts: Veteran participants will receive text messages, with messages chosen to align with their selected storyteller. These texts will be delivered using the VA HealtheDialog texting system, described above. In the baseline phone visit, Veterans will receive an orientation to the texting system, over the phone. RAs will enroll Veterans in HealtheDialog and provide education on use of the system and what to expect from the CTC protocol.

- Procedure for Control Group Participants:

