Veterans will have an over-the-phone visit during which the RA enrolls each Veteran in the control texting protocol and collects baseline data including blood pressure and all Baseline elements described in Section 5.5. Veterans will then receive 6 months of text messages, receiving one assessment text weekly with a follow-up reminder if needed, and they will also receive responses to their reply to assessment texts.

CTC Texting Protocol (content and tasks required from participant):

- Narrative-aligned Texts (“Storyteller Texts”): Participants will be invited to choose the Veteran storyteller whom they found most compelling; this choice will then be used to guide selection of a longitudinal texting protocol designed to ‘continue the conversation’ over a six-month period. Storyteller texts are intended as cues, triggering recollection of the foundation laid through the initial story viewing. Our intention is to use these texts to engage participants on both an emotional and cognitive level. We will adapt transcribed content from our VA Stories videos to create narrative-aligned texts (“storyteller texts”) (Appendix 3). Adaptation of transcribed content will be conducted with 3 goals: to identify quotations for which (1) the clarity and length are conducive to incorporation into a stand-alone text message, (2) content maps to our conceptual model and (3) to ensure that quotations convey the storyteller’s ‘voice’ (their own words/phrases). Where direct quotations conducive to incorporation into text are not available, narrative-aligned texts will convey messages that reference and build upon the story content.
- Our team has already completed qualitative analyses of full (unedited) video recordings of Veteran narrators. Completed analyses identified story segments guided by storytelling best practices and informed by constructs from our conceptual model; this work will inform our selection of content for storyteller texts.

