5.5 Study Evaluations

- We will pilot the process of (1) guiding the Veteran in at-home BP check; (2) selection of a preferred veteran storyteller after viewing all stories; (3) using this choice to inform selection of a texting protocol; (4) Receipt of 1 month of texts; and 5) follow-up assessment at the end of 1 month. Research assistants will collect field notes on items (1) (2) and (3). For item (4) we will collect data on implementation/process measures throughout the 4-week period (see Table 8 below, item 7 for details of these measures). We will also assess feasibility of two options for Veterans to access texts: (a) via regular texting, available on all text-enabled phones; (b) via HealtheDialog 'App' which allows study team tracking of text opening (but is available only on Smart phones).
- All data will be stored in accordance with VA policy.
- Only the study team and the PI will have access to this information.

For the randomized controlled trial, as listed in the table below, we will collect 7 data elements: (1) Veteran characteristics; (2) Intervention dose/exposure; (3) Narrative Communication measures; (4) Social Cognitive-Theory-based measures; (5) Hypertension management behaviors; (6) Blood Pressure (BP) (blood pressure will be checked by participant through home BP monitor at baseline and at 6 month follow up); and (7) Implementation Data including Process Measures and measures of Fidelity. We will gather these elements through initial data collection (CDW), over-the-phone screening survey, baseline visit and follow-up visit observations and surveys, texting system and phone calls to participant.

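### The primary blood pressure model leaves the baseline group difference free; a common baseline mean, or adjustment for baseline BP, would cut the variance by 22% on the SAP's own inputs

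*SAP*

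**What the plan says.** The SAP (Analysis Plan, Hypothesis 1) frames H1 as a difference-in-differences: "We will use study group, assessment time, and group-time interactions as predictors in regression models". The group-by-time coefficient is the treatment effect. Because the model has a group main effect, the baseline difference between arms is a free parameter.

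Other adjustment is secondary and depends on what is observed. The same section says the models will "adjust for observed group imbalances as secondary analyses". The SAP section on covariates names demographic and behavioural variables, not baseline BP. Baseline BP is otherwise used only in a secondary analysis split at the median baseline mean arterial pressure. No primary analysis conditions on it or sets the baseline means equal.

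Four other statements matter here:
- Missing data (SAP): "We will use all available data regardless of whether a patient has a complete record". Participants with only a baseline reading therefore stay in the model.
- Randomisation (SAP): "Random allocation to CTC or control will be stratified by site, and within each site, we will stratify by sex (women/men".
- Power inputs (SAP, Power Calculations; repeated in Protocol 5.6): "85% follow-up, correlation = 0.5, SD = 18 (equivalent to variance of 324".
- Measurement: the SAP (Data Collection) has the research assistant take BP in person, whereas Protocol 5.5 says "blood pressure will be checked by participant through home BP monitor at baseline and at 6 month follow up".

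**The concern.** In a randomised trial the true baseline difference is zero if baseline BP is measured before allocation can influence it. A model that estimates this difference freely and subtracts it carries the sampling error of a quantity already known. Imposing a common baseline mean, or conditioning on baseline BP, removes that error. Under randomisation the target is the same: the between-arm difference in change to 6 months.

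What is at stake is precision from data already collected. The cost grows as the within-person correlation (rho) falls. The value 0.5 comes from the sponsor's prior work, and the SAP states it alongside in-person readings. The Protocol has moved to self-measured home readings and repeats 0.5 without a separate value for them. The SAP also reports that an earlier trial's adjusted systolic difference was as low as 2.7 mm Hg, so spare power at 5 mm Hg does not make precision unimportant.

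**Working it through.** **Inputs.** From SAP Power Calculations: SD 18 (variance 324), rho 0.5, 85% follow-up (82% as the alternative), 600 participants, difference 5 mm Hg, two-sided alpha 0.05. Assumed: 1:1 allocation (the ratio is not stated), giving N = 300 per arm at baseline and n = 255 at 6 months (246 at 82%); equal SD at both times; one reading per time; equal follow-up in both arms; follow-up missing at random given baseline. Power uses the normal approximation; the detectable difference at 80% power is 2.80 × SE.

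**The plan's own figure.** A change score in completers has SD 18 × √(2 × (1 − 0.5)) = 18 and SE 18 × √(2/255) = 1.594. Power is 88.0% at 85% follow-up and 86.9% at 82%. Both agree with the SAP's claim of more than 80%.

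**Planned model, all available data.**

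Var = 2 × 324 × [(1 − rho²)/n + (1 − rho)²/N] = 648 × [0.75/255 + 0.25/300] = 2.446

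SE 1.564; power 89.2%; detectable difference 4.4 mm Hg.

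**Common baseline mean, or 6-month BP adjusted for baseline BP.**

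Var = 2 × 324 × (1 − rho²)/n = 648 × 0.75/255 = 1.906

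SE 1.381; power 95.2%; detectable difference 3.9 mm Hg.

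**Comparison.** 1 − 1.906/2.446 = 22.1% lower variance. Sample size for the planned model to match: 600 × 2.446/1.906 = about 770. The 95% interval narrows from 2 × 1.96 × 1.564 = 6.1 mm Hg wide to 2 × 1.96 × 1.381 = 5.4. A simulation of 10,000 trials gave a 22.2% reduction. The familiar figure of 25% applies to complete pairs; 22% is the fair figure because the SAP keeps baseline-only participants.

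At 82% follow-up the SEs are 1.586 and 1.406, power is 88.3% and 94.5%, and the variance is 21.5% lower.

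**Other values of rho** (assumed; SD 18, 85% follow-up):

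| rho | Planned SE | Planned power | Common-baseline SE | Common-baseline power | Variance reduction |
|---|---|---|---|---|---|
| 0.3 | 1.836 | 77.7% | 1.521 | 90.8% | 31% |
| 0.4 | 1.707 | 83.4% | 1.461 | 92.8% | 27% |
| 0.5 | 1.564 | 89.2% | 1.381 | 95.2% | 22% |
| 0.7 | 1.221 | 98.4% | 1.138 | 99.2% | 13% |

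**A smaller true effect.** At 2.7 mm Hg and rho 0.5, power is 41% as planned and 50% with the common baseline.

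**Site and sex.** With assumed level differences of 4 mm Hg between sites and 3 mm Hg between sexes, and 20% women, adding both leaves the planned SE at 1.564 and moves the common-baseline SE only from 1.381 to 1.378. The gain comes from baseline BP.

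**The case against.** The strongest reply is that nothing is broken. Hypothesis, model and power calculation all use the same difference-in-differences, and power is 89.2% against a target of 80%. That is correct, and the figure of 770 is an equivalence, not a shortfall. It does not remove the gain in interval width.

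The planned model falls short only in an assumed case. Neither document suggests rho 0.3, and a change in how BP is measured could alter the SD as well. With SD 18 the planned model drops below 80% only when rho is under about 0.34; at rho 0.3 with an assumed SD of 17 it has 82.2%. This stands: the rho 0.3 result is a sensitivity case that holds SD at 18.

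The exact 22% depends on equal SDs. At rho 0.5, assumed SDs of 17 at baseline and 19 at 6 months give 15%; the reverse gives 30%. The SAP gives a single SD, so 22% is right on its inputs, but the direction is firmer than the figure. Both documents also list the VA data warehouse as a BP source, and Protocol 5.6 would pull those data for the whole participation period. If such values enter the primary analysis, the two-reading calculation changes.

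The most substantive objection concerns the equal-baseline condition. Protocol 5.1 says intervention participants are "told during the baseline visit, once assigned to intervention" about storyteller assignment, and for controls that "the RA enrolls each Veteran in the control texting protocol and collects baseline data including blood pressure". Allocation and a self-measured reading thus share a visit, with no order given. Table 8 separates baseline from post-video measures but does not place the reading relative to allocation. The planned model does not assume equal baseline means, so the improvement is conditional on that order.

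**Conclusion.** The point holds. The primary H1 model gives up precision that the trial can have without new data: on the SAP's inputs its variance is 2.446 against 1.906, a 22% reduction, and power at 5 mm Hg would rise from 89.2% to 95.2%. The gain runs from 31% at rho 0.3 to 13% at rho 0.7. This is inefficiency in a valid plan, and the change is recommended rather than essential. The figures rest on 300 per arm, one SD of 18 at both times, two readings per participant, equal follow-up and missingness at random given baseline. The common-baseline model further requires that knowledge of allocation could not affect the baseline reading.

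**What to change.** - Make the primary H1 analysis the longitudinal model with a common baseline mean: time and group-by-time, with no group effect at baseline. This keeps the commitment to all available data. Regressing 6-month BP on arm and baseline BP has the same SE here, but it drops participants without a 6-month reading and so fits that commitment less well.
- Prespecify site and sex as covariates so that the analysis follows the stratified randomisation. Expect little change in SE.
- Keep the unconstrained difference-in-differences as a sensitivity analysis and imbalance-driven adjustment as secondary.
- State that baseline BP is recorded before allocation is revealed. If this cannot be confirmed, report the unconstrained estimate beside the constrained one.

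The cost is SAP wording and one sentence on the order of events at the baseline visit. Baseline BP, site and sex are already collected. The choice should be fixed before outcome data are seen, so that it cannot look driven by the results.
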